Open-Label Randomized Controlled Trial to Assess Preoperative Acupuncture for Patients Undergoing Total Knee or Hip Arthroplasty

OVERVIEW

Acupuncture has been extensively practiced and studied worldwide, particularly as a part of Eastern medicine, but it is a relatively uncommon therapy offered in Western medical institutions, such as those in the United States. Considering the commonly cited benefits of acupuncture, such as reduced anxiety and pain, hospitals throughout the United States have the opportunity to implement acupuncture as a cost-effective and safe technique for improving surgical outcomes.

Acupuncture administered in the preoperative period can be particularly effective for reducing preoperative anxiety, postoperative pain, postoperative opioid consumption, and postoperative nausea and vomiting. Consequently, preoperative acupuncture can improve patient satisfaction and decrease hospital costs. However, due to lack of implementation and experience, further research is needed to establish the safety and efficacy of preoperative acupuncture in the United States medical practices.

At the Bone-and-Joint Institute at Hartford Hospital, where this study is proposed, a quality study on total knee or hip arthroplasty patients found that 21% of its monthly patients were “high-anxiety” according to the Amsterdam Preoperative Anxiety and Information Scale (APAIS). Thus, there is a significant population of patients that would benefit from a procedure to reduce preoperative anxiety at our facility.

This proposal is for a prospective, open-label, randomized controlled trial to determine the effect of preoperative acupuncture on preoperative anxiety and postoperative pain for high-anxiety patients undergoing total hip arthroplasty or total knee arthroplasty. We hypothesize that preoperative acupuncture will reduce preoperative anxiety and postoperative pain as well as reduce postoperative nausea and vomiting and opioid consumption and improve patient satisfaction. The study population is to include adult patients undergoing lower extremity total joint arthroplasty, including of the hip and knee joints, at the Bone-and-Joint Institute at Hartford Hospital.

Table of Contents

OVERVIEW	1
1.0 OBJECTIVES AND SCIENTIFIC AIMS	3
2.0 BACKGROUND AND RATIONALE	3
3.0 OVERVIEW OF STUDY DESIGN/INTERVENTION	5
3.1 Design	5
3.2 Randomization	5
3.3 Acupuncture Intervention	5
3.4 Therapy Materials	6
4.0 CRITERIA FOR SUBJECT ELIGIBILITY	6

1.0 OBJECTIVES AND SCIENTIFIC AIMS

Primary Objectives: In patients with high anxiety undergoing THA or TKA:

- 1) Determine if preoperative acupuncture reduces preoperative anxiety in the acupuncture group.
- 2) Examine postoperative pain following acupuncture compared to control.

Secondary Objective: To determine the safety of preoperative acupuncture by recording complications throughout hospital length of stay; to determine whether preoperative acupuncture reduces postoperative nausea and vomiting, reduces postoperative opioid consumption, reduces anxiolytics need during hospitalization and improves satisfaction compared to control in high-anxiety patients undergoing THA or TKA.

2.0 BACKGROUND AND RATIONALE

Acupuncture has been a practice of Chinese medicine for over 2,500 years for treating diseases, relieving pain, and more recently for improving the outcomes of surgery.^[1] In the United States, however, acupuncture was relatively unheard of as a medical practice until the 1970s, and the nation has since remained hesitant to implement it in the hospital.^[2] As a result, while the research on acupuncture shows potential benefits for both patients and providers, most of these studies have been conducted outside of the United States, which likely has contributed to the nation's cautious stance. Practitioners and researchers, therefore, need to demonstrate and determine whether the touted benefits of acupuncture can be extended to practices in the United States.

Postoperative pain is commonly studied as a primary outcome of acupuncture treatment, and improvements in pain are often cited as a benefit.^[3-11] For example, in a large study that aimed to evaluate an acupuncture rehabilitation program on 2,282 patients who underwent total knee arthroplasty (TKA) or total hip arthroplasty (THA), patients on average reported a 45% reduction in pain following acupuncture treatment.^[3] Another study randomized 80 patients who received TKA to receive either postoperative acupuncture treatment or standard rehabilitation care, and results showed that patients in the acupuncture group experienced significantly reduced postoperative pain, increased knee range-of-motion, and faster rehabilitation time.^[7] Heightened postoperative pain is, understandably, a strong predictor of worsened surgical outcomes and patient dissatisfaction, and, according to a systematic review of nearly 30,000 TKA patients, the most consistent predictor of postoperative pain is preoperative pain.^[12] Therefore, perhaps the best method for improving surgical outcomes and patient satisfaction is to target both postoperative and preoperative pain. Since few studies have explored the analgesic effects of acupuncture in the preoperative period, there is an opportunity for future research to determine whether the pain-reducing effects of acupuncture can be used in the preoperative period to improve surgical outcomes and patient satisfaction.

Intra- and postoperative opioid consumption is another commonly studied outcome of acupuncture.^[13] In a randomized controlled trial (RCT) of 54 patients receiving THA, researchers randomized patients to receive either auricular (of the ear) or sham acupuncture treatment and compared the amount of piritramide (a synthetic opioid closely related to fentanyl and commonly used in European countries) used

intraoperatively.^[9] The results showed that patients in the acupuncture group required significantly less piritramide intraoperatively compared with sham (37 ± 18 mg vs. 54 ± 21 mg). A similarly constructed RCT also studied the effects of preoperative auricular acupuncture on intraoperative opioid use, but researchers instead studied fentanyl use and included patients undergoing TKA.^[14] These researchers, too, found that patients in the acupuncture group required significantly less opioid during surgery than patients in the sham acupuncture group (620.7 ± 258.2 μ g vs. 868.6 ± 319.3 μ g). Further, these patients on average lasted longer before requesting analgesia and exhibited lower visual pain scores. Several other studies have also demonstrated that preoperative acupuncture lessens the need for opioids during and after surgery.^[4,10,15,16] Reducing opioid consumption through the introduction of safely administered acupuncture poses a potential net improvement for patient safety and hospital costs.

Perhaps the most commonly cited benefit of acupuncture is increased relaxation and decreased anxiety, and several systematic reviews have reported that these benefits persist in the clinic.^[1,3,17] For patients with anxiety, depression, or other mental ailments, this is an important finding considering the substantial evidence linking poor mental health with significantly worse surgical outcomes.^[18-27] For example, one systematic review that accounted for 53,562 patients undergoing THA concluded that depression and anxiety were associated with increased postoperative pain, and another that accounted for 95,560 patients undergoing TKA found that the most consistent and significant indicator of dissatisfaction related to surgery was preoperative anxiety.^[27,28] Despite this evidence that poor preoperative mental health is detrimental to both practitioners and patients of surgery, there are currently no guidelines for improving preoperative mental health conditions.^[25]

Preoperative acupuncture can serve as an ideal therapy to safely reduce preoperative anxiety and improve surgical outcomes. It has been repeatedly demonstrated as a safe, cost-effective, and time-effective procedure for reducing preoperative anxiety, postoperative pain, total opioid consumption, and postoperative nausea and vomiting while increasing patient satisfaction.^[4,13,29] However, medical practices in the United States have largely forgone the potential upsides of acupuncture due to minimal existing research undertaken within the country. Therefore, there is an opportunity for United States medical researchers and practitioners to demonstrate the potential for preoperative acupuncture as a safe and effective therapy to improve surgical outcomes for both patients and providers.

This proposal suggests a robust study to evaluate the safety and efficacy of preoperative acupuncture performed on high-anxiety patients undergoing THA or TKA at the Bone-and-Joint Institute (BJI) at Hartford Hospital. Evidence suggests that the outcomes of THA and TKA in particular are associated with preoperative anxiety and postoperative pain.^[30] Patients will be classified as high-anxiety based on having an APAIS-A-T (Appendix I) score greater than 10, a threshold used in previous studies.^[31-34]

3.0 OVERVIEW OF STUDY DESIGN/INTERVENTION

3.1 Design

This is a prospective, open-label, randomized controlled trial to determine the efficacy and safety of preoperative acupuncture on high-anxiety patients undergoing TKA or THA. Patients scheduled for THA or TKA to be performed by one of the IRB approved orthopedic surgeons at the BJI will be screened for high preoperative anxiety one week prior to procedure in the PREPARE Center, the BJI's preoperative services clinic, using printed copies of the APAIS questionnaire. The APAIS will be used as a screening tool and is considered optional for the patient to complete and not a standard of care measure. High-anxiety patients consenting to the study will be randomized to receive either 1) preoperative acupuncture (Acupuncture) or 2) no intervention (Control). Results from a quality study at the PREPARE clinic demonstrates that number of patients with high-anxiety entering the clinic is 30 per month. Accounting for the availability of investigators and surgeons, the study period is estimated to last approximately two years to obtain the 50 patients, 25 per group that we aim to enroll in this study. There will be an interim analysis after enrolling 14-15 patients in each group (60%) to re-estimate the sample size using more appropriate data (see sample size estimate section). Each patient will be enrolled in the study from the time of consent and will be followed up to 30 days postoperatively. Investigators performing the acupuncture will be licensed and certified throughout the study duration.

3.2 Randomization

Patients will be randomized immediately following the consenting process. Randomization will be achieved using a random number generator, which will randomly produce a 0, representing the Acupuncture group, or a 1, representing the Control group, for each patient. Patients will immediately be informed, for their convenience, of their group assignment given the non-blinded nature of the trial.

3.3 Acupuncture Intervention

Prior to acupuncture treatment, all patients in the acupuncture group will receive a medical assessment including a review of the patient's medical chart. The acupuncture intervention will include a combination of auricular and body acupuncture. The auricular points used will include: Shen men, Zero point, Tranquilizer point and Master cerebral. The body point will be the wrist acupuncture point PC6. All points will be bilateral. With the patient seated, body and auricular points will be wiped with 70% isopropyl alcohol wipes. After about 1 minute of drying, the acupuncture needles will be inserted. The needles used on both ear and wrist points will be the DBC Detox-5 needles. They will be retained for approximately 20 minutes, removed and placed into a sharps container.

3.4 Therapy Materials

- Alcohol wipes
 - Disposable, individually sealed alcohol preppads
 - Each pad is saturated with 70% isopropylalcohol
 - 1" x 2.5"
- Acupuncture needles
 - 1) SEIRIN J-Type Acupuncture Needles (SKU: SJ.18X30; Figure 1)
 - Length: 30 mm
 - Diameter: 0.18 mm
 - 2) SEIRIN J-Type Acupuncture Needles (SKU: SJ.20X30)
 - Length: 30 mm
 - Diameter: 0.20 mm
 - 3) DBC™ Detox-5 Acupuncture Needles (SKU: DTX.20X13; Figure 2)
 - Length: 13 mm
 - Diameter: 0.20 mm

Figure 1. Seirin needles (SEIRIN® (SKU: SJ.18X30)

Figure 2. DBC™ Detox-5 Acupuncture Needles (SKU: DTX.20X13).

4.0 CRITERIA FOR SUBJECT ELIGIBILITY

4.1. Subject Inclusion Criteria

- Female or male patients undergoing TKA or THA surgery at the Bone-and-Joint Institute at Hartford Hospital
- High-anxiety (APAIS-A-T >10)
- Age: 52 to 85

4.2. Subject Exclusion Criteria

- Unable to give consent
- Uncontrolled diabetes (HbA1c \geq 8.0%)
- Infection at any of the acupuncture points
- Known allergy to metals
- Abnormal laboratory blood work values (INR >1.5, if available; platelet count <70,000, if available)
- Patients with active ongoing coagulopathy based on lab data (INR >1.5) and/or on current anticoagulant use which increases bleeding risk.
- Women in reproductive age or under the age of 52 years old, as acupuncture is not recommended with pregnancy
- Non-English speaking
- Revision TKA or THA

5.0 RECRUITMENT PLAN

Potential patients who are scheduled for either TKA or THA will receive the APAIS questionnaire form with the other preoperative forms that they are typically receiving through Force Therapeutic platform 30 days prior to their scheduled surgery date. A

member of the study personnel will receive the completed APAIS and will screen potential subjects for the other eligibility criteria using our electronic medical record (EMR) system (EPIC). The study personnel will notify PREPARE providers of high-anxiety patients a day prior to their PREPARE visit to plan to keep those patients in a separate room for consenting. A member of the study personnel will meet with the potential subjects for consenting after they complete their visit with the provider. During the consenting process, patients will be informed of the study details, benefits, risks, and enrollment process and will be given necessary time for questions and concerns. Specifically, patients will be made aware that this is a randomized trial and that they will, therefore, be randomized to one of two study groups. Patients providing consent will be enrolled in the study.

If the consenting process cannot be conducted in-person, the same discussion of consent will be conducted via video call or by telephone, following the Hartford Healthcare (HHC) consenting guidelines, and the link to the electronic consent form will be sent via email using an HHC-licensed Research Electronic Database Capture (REDCap) database.

For enrolled patients, two signed consent forms will be printed, of which one will be stored in a patient binder, and the other will be given to the patient on the day of surgery. Documentation of the consenting process and the printed consent form will be scanned and uploaded to EPIC. Enrolled patients will be registered into a study-specific REDCap database and given a unique study ID number along with their randomly assigned study group. A linkage file will be created connecting the patient study IDs to their corresponding medical record numbers (MRNs), and this file will be stored on a secured, password-protected HHC server.

6.0 PRETREATMENT EVALUATION

Baseline preoperative history and physical exam evaluations from the PREPARE clinic of the Bone-and-Joint Institute will be used to collect the clinical demographic variables listed below. Laboratory tests, shown below, are also recommended, and corresponding results will be gathered if they occurred within 60 days prior to surgery.

Clinical Demographic Variables of Interest

- Age
- Gender
- Race and ethnicity
- BMI
- History of bleeding disorders
- History of coagulopathy
- History of acupuncture treatment
- Uncontrolled diabetes mellitus
- Present infection at the sites of acupuncture
- History of mental illness
- History of TKA or THA surgery
- Known allergy to metal

- INR (if available)
- Platelet count (if available)

7.0 INTERVENTION ORDER OF EVENTS

7.1 Acupuncture Group

1. On the day of surgery and prior to procedure, study patients will be waiting in the preoperative area.
2. The patient will be placed in bay #1 or other bay if #1 is not available in the preoperative area.
3. A member of the study personnel will assess the patient's baseline anxiety and pain.
4. The assigned acupuncturist will conduct a preoperative medical assessment and chart review on the patient prior to intervention.
5. The patient will then undergo the acupuncture procedure given by the assigned acupuncturist.
6. Anxiety and pain will be reassessed by a member of the study personnel after the procedure.
7. The patient will undergo their surgical procedure.
8. The patient will be reevaluated for pain three times; when they arrive to the post-anesthesia recovery unit (PACU), after an hour, and after 3 hours.
9. The patient will be reevaluated for PONV/Impact score two times; after an hour from their arrival to the post-anesthesia recovery unit (PACU), and after 3 hours. Postoperative antiemetics used will also be collected from the patient's chart retrospectively, following enrollment.
10. Postoperative opioid consumption and anxiolytics used throughout hospitalization will be collected from the patient's chart retrospectively, following enrollment.
11. Admission and discharge dates & times will be collected directly from the patient's chart retrospectively, following enrollment and used to determine total hospital length of stay.
12. Patient satisfaction regarding surgery will be evaluated within a week after the discharge from the hospital.

7.2 Control Group

1. On the day of surgery and prior to procedure, study patients will be waiting in the preoperative area.
2. The patient will be placed in bay #1 or other bay if #1 is not available in the preoperative area.
3. A member of the study personnel will assess the patient's baseline anxiety and pain.
4. The patient will undergo their surgical procedure.
5. The patient will be reevaluated for pain three times; when they arrive to the post-anesthesia recovery unit (PACU), after an hour, and after three hours.
6. The patient will be reevaluated for PONV/Impact score two times; after an hour from their arrival to the post-anesthesia recovery unit (PACU), and after 3 hours. Postoperative antiemetics used will also be collected from

- the patient's chart retrospectively, following enrollment.
7. Postoperative opioid consumption and anxiolytics used throughout hospitalization will be collected from the patient's chart retrospectively, following enrollment.
 8. Admission and discharge dates & times will be collected directly from the patient's chart retrospectively, following enrollment and used to determine total hospital length of stay.
 9. Patient satisfaction regarding surgery will be evaluated within a week after the discharge from the hospital.

8.0 OUTCOME EVALUATION

All outcomes will be measured during the time periods illustrated in Table 1 using the following measurement methods:

- PreOP anxiety: Amsterdam Preoperative Anxiety and Information Scale (APAIS; Appendix I)
- State anxiety: Visual Analogue Score (VAS; Appendix VI) will be compared between pre and post acupuncture in the same patient within the acupuncture group.
- State anxiety: Visual Analogue Score (VAS; Appendix VI) preop anxiety assessment will be compared between the two groups to assess their baseline preop anxiety status on day of surgery.
- Pain: 11-point Numeric Pain Rating Scale (NPS; Appendix V) will be compared between the two groups
- Postoperative opioid consumption: collected through EPIC and converted into morphine milligram equivalents (MMEs) using Appendix IV. This will be compared between the two groups. Postoperative nausea and vomiting (PONV): PONV impact score (Appendix VII) will be compared between the two groups. Additionally, postoperative antiemetics needed during hospital admission will be collected directly from EPIC and compared between the two groups.
- Satisfaction with surgery: questionnaire (Appendix III) provided by a member of the study personnel by phone within a week after the discharge from the hospital.
- Adverse events related to the interventions will be recorded throughout enrollment.
- Anxiolytics medication needed throughout hospitalization will be collected directly from EPIC and compared between the two groups.
- Hospital length of stay will be collected directly from EPIC using hospital admission and discharge dates & times; this will be compared between the two groups.

Table 1. Outcome measurement time, researcher-to-patient interface, and method for all study outcomes.

[figure not shown]
Time	Interface	Outcome/ Measurement (Acupuncture)	Outcome/ Measurement (Control)
-10 to -7 days	PREPARE Center	
 • Preoperative anxiety/APAIS 	
 • Preoperative anxiety/APAIS

HHC-IRB
 IRB NUMBER: HHC-2021-0348
 IRB APPROVAL DATE: 06/02/2023

PreAQ/PreOP	Holding bay	
 • Anxiety/VAS • Pain/NPS • Anxiolytics 	
 • Anxiety/VAS • Pain/VAS • Anxiolytics
PostAQ/PreOP	Holding bay	
 • Anxiety/VAS • Pain/NPS 	NA
PostOP	PACU: on arrival, 1 hour, and 3 hours	
 • Pain/NPS • Anxiolytics 	
 • Pain/NPS • Anxiolytics
PostOP	PACU: 1 hour, and 3 hours after arrival	
 • PONV/impact score 	
 • PONV/impact score
PO-Discharge	chart review	
 • Opioid use/MME • Anxiolytics • Antiemetics • Hospital length of stay 	
 • Opioid use/MME • Anxiolytics • Antiemetics • Hospital length of stay
Within a week from discharge	Phone call	
 • Satisfaction questionnaires 	
 • Satisfaction questionnaires

Abbreviations: NPS, numeric pain rating scale; PACU, post-anesthesia care unit; PONV, postoperative nausea and vomiting; POD, postoperative day.

Figure 3. Protocol schema.

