10.0 PROTECTION OF HUMAN SUBJECTS

Every effort will be made to ensure the safety of our patients and the confidentiality of their medical information. During the enrollment and consent process, all risks, benefits, side effects, and alternatives will be discussed. Also, it will be stressed that this is a voluntary study and that the patient can withdraw without prejudice at any time.

Benefits

The potential benefit of this study is that preoperative acupuncture is effective in reducing preoperative anxiety and postoperative pain in patients undergoing lower extremity total joint arthroplasty. Such a reduction in postoperative pain and anxiety could potentially increase overall patient satisfaction. Further, patients will not be compensated for participating in this study, but they will receive the acupuncture service at no cost.

Risks

The risks of participation include the risks associated with performing acupuncture include, but are not limited to, the following: minor bleeding, pain, pneumothorax, abdominal injuries, heart injuries, CNS injuries, neck injuries, eye injuries, peripheral nerve injuries, and infection.

Alternatives

The alternative to acupuncture for addressing high-anxiety patients is the standard of care. For pain, this includes the use of standard pain medications, including opioid and non-opioid analgesics, in addition to regional blocks. For anxiety, this includes the regular use of anxiolytic medications and psychological consultation referrals. These standard-of-care procedures will not be replaced by acupuncture and rather performed in adjunct. A patient's decision on whether or not to participate in this study will not affect the availability of standard and supportive measures.

Costs

There will be no additional cost incurred by the participant to participate in the study.

Acupuncture materials and service will be provided at no additional cost to the patients enrolled in the study and will be provided by one of the study investigators.

Voluntary Nature of Study

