For the primary aim *pain*, based on data from the first 31 patients enrolled, our sample size calculation indicates that a minimum of 26 subjects per group are needed using a repeated measures design (each subject is measured 4 times) with 2 groups for a total of 52 subjects. This design achieves 81% power to test factor B1 if a Geisser-Greenhouse Corrected F Test is used with a 5% significance level and the actual effect standard deviation is 0.255 (an effect size of 0.40319). We estimate an attrition rate of 10%, which will require 58 subjects; however we will aim to enroll 60 subjects (30 per group). For the second primary aim *anxiety*, we performed two sample size calculations. One based on the data of all 17 patients in the acupuncture group, and another excluding the 3 patients for which protocol deviations were reported due to methods collecting the anxiety measure. With all 17 patients, the difference in the response of anxiety from pre to post acupuncture was normally distributed with a standard deviation 26.27. If the true difference in the mean response of matched pairs is 35.64, we will need to study 6 pairs of subjects to be able to reject the null hypothesis that this response difference is zero with probability (power) 0.8. The Type I error probability associated with this test of this null hypothesis is 0.05. With the 3 patients removed, the difference in the response of anxiety from pre to post acupuncture was normally distributed with standard deviation 26.588. If the true difference in the mean response of matched pairs is 39.14, we will need to study 6 pairs of subjects to be able to reject the null hypothesis that this response difference is zero with probability (power) 0.8. The Type I error probability associated with this test of this null hypothesis is 0.05.

Pain is the more appropriate primary outcome of the two primary outcomes to base the sample size on because there are 4 time points of data for each group for this variable. The other primary outcome, *anxiety* does not have a post measure for the control group (per the study design), and therefore a within-group pre to post change in the acupuncture group is being performed to examine this outcome. We acknowledge that this within group design is weaker than the design to assess the pain outcome measure.

Statistical Methods

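### The primary within-arm anxiety change takes no account of when an anxiolytic was given relative to the two VAS ratings, so a drug effect arising between them could be counted as acupuncture effect

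*Combined protocol and SAP*

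**What the plan says.** Section 1.0 words the first primary objective causally: "Determine if preoperative acupuncture reduces preoperative anxiety in the acupuncture group". Section 8.0 measures it with a VAS that "will be compared between pre and post acupuncture in the same patient within the acupuncture group". Section 11.0 (Sample Size) confirms that "a within-group pre to post change in the acupuncture group is being performed to examine this outcome" and concedes that this is weaker than the pain comparison, because controls have no second measure.

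On anxiolytics, section 10.0 (Alternatives) describes standard care: "For anxiety, this includes the regular use of anxiolytic medications and psychological consultation referrals". It adds: "These standard-of-care procedures will not be replaced by acupuncture and rather performed in adjunct". In the acupuncture column of Table 1, the PreAQ/PreOP holding-bay row reads "Anxiety/VAS • Pain/NPS • Anxiolytics". The PostAQ/PreOP row has anxiety and pain only.

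The order of events in 7.1 runs from baseline rating to medical assessment and chart review, acupuncture, and then the second rating: "Anxiety and pain will be reassessed by a member of the study personnel after the procedure". It says nothing about anxiolytic timing. The one stated use of the anxiolytic data is as an outcome: "Anxiolytics medication needed throughout hospitalization will be collected directly from EPIC and compared between the two groups". The Statistical Methods in 11.0 name no covariate, exclusion or sensitivity analysis for doses given before the second VAS.

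**The concern.** Every participant is enrolled for high anxiety, standard care for anxiety includes drugs, and that care runs alongside acupuncture. Section 3.3 has the needles in place for about 20 minutes. Assessment, chart review and skin drying add to the gap between ratings, so there is time for a drug to be given or to take effect.

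If that happens, the patient's whole fall in VAS enters the primary result as response to needling. In a two-arm comparison of change, a drug used equally in both arms would largely cancel. Here nothing can cancel it, because the control arm has no second rating. At stake is what objective 1 can conclude: a real and significant fall may be partly a drug effect, and the planned data would not let a reader tell how much.

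**Working it through.** **1. Reproducing the plan's figures.** Inputs from 11.0: mean change 35.64, SD 26.27 (17 patients); mean 39.14, SD 26.588 (3 protocol deviations removed); two-sided alpha 0.05; power 0.80. With a paired t-test and the noncentral t distribution:
- 35.64/26.27: power is 0.757 with 6 pairs and 0.846 with 7, so 7 pairs.
- 39.14/26.588: power is 0.819 with 6 pairs, so 6 pairs.

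The plan states 6 in both cases, which agrees to within one pair. For the 17 patients, t = 35.64 / (26.27/√17) = 5.59, and the 95% interval is 35.64 ± 13.51, or 22.1 to 49.1. Sample size is not the problem. What the change can be attributed to is.

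**2. What a dose between ratings would add.** Let p be the share dosed between the ratings and m the mean VAS fall due to the drug. Neither is in the documents, so both are assumed, as is a 0–100 VAS. The addition to the mean change is p × m, and its share of the interim change is p × m / 35.64. The last column is the chance of p < 0.05 if acupuncture, and everything else apart from the drug, had no effect. It uses 27 pairs (30 planned less 10% attrition) and SD held at 26.27.

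| p | m | p × m | Share of 35.64 | Chance of p < 0.05 |
|---|---|---|---|---|
| 10% | 10 | 1.0 | 3% | 5.4% |
| 10% | 20 | 2.0 | 6% | 6.7% |
| 25% | 20 | 5.0 | 14% | 15.9% |
| 50% | 20 | 10.0 | 28% | 47.8% |
| 50% | 40 | 20.0 | 56% | 96.8% |
| 75% | 30 | 22.5 | 63% | 99.0% |

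The scenarios run from negligible to dominant, and the planned data would not show which one applies.

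**3. Direction.** A drug that takes effect between the ratings enlarges the fall. A drug already acting at the first rating lowers that rating and can shrink the fall. The only preoperative anxiolytic entry in Table 1 sits with the first rating, so the second case cannot be dismissed. The sign depends on dose time relative to both ratings.

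**4. What the sensitivity analyses can deliver.**

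*Zero change for patients dosed between ratings.* With undosed mean μ and SD s, the mean is (1−p)μ and the SD is √[(1−p)(s² + μ²) − ((1−p)μ)²].
- If undosed patients really average 35.64 (s = 26.27), power with 27 pairs is above 99.9%, 99.5% and 93.3% for p = 10%, 30% and 50%.
- If drugs inflated the interim mean, undosed patients fell by less: μ = 35.64 − p × m. At p = 50% and m = 20, μ = 25.64 and the zero-assigned mean is 12.82. Power is 81% with s = 26.27, or 85% if the dosed/undosed variance p(1−p)m² is first taken out of s².
- At p = 50% and m = 40, μ = 15.64 and the mean is 7.82. Power is 49% or 78% on the same two bases.

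*Undosed patients only.* The 95% half-width is t × 26.27/√n. For 27 patients it is 2.056 × 26.27/√27 = 10.4 points. For 14 (about half dosed) it is 2.160 × 26.27/√14 = 15.2 points.

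**The case against.** The strongest reply is that nothing in the documents shows a drug being given between the ratings. Section 10.0 describes standard care in general, without time or place. The steps in 7.1 contain no drug. The absence of anxiolytics from the PostAQ row may mean that none are expected then. The protocol schema (Figure 3) is not visible in the text available. All of this stands, and it is why the point says that a drug effect could be counted, not that it is. It does not close the gap: anxiolytics are an explicit holding-bay entry, and no step ties their timing to the outcome.

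A second reply is that 11.0 already admits the design is weaker. That admission concerns the missing control measure and does not mention concomitant drugs, although they are one of the uncontrolled influences that it implies.

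A third is that change under usual care, drugs included, is a legitimate quantity. That also stands, and it is the reason to leave the all-patients change as the main analysis. It does not support the causal wording of objective 1.

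A reader might infer three stronger things, none of which the documents support:
- *The bias always favours acupuncture.* It does not; see step 3.
- *Zero assignment should become the main analysis because it removes the bias.* It imposes an assumption of no acupuncture effect in those patients and turns any worsening into no change. It would also change a primary analysis after the interim pre/post data were examined.
- *Power is ample whatever the drug did.* That holds only if the 35.64-point mean is uninflated; see step 4.

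**Conclusion.** The gap is real. A causal primary objective rests on an uncontrolled pre/post VAS change, anxiolytics are allowed for in the same setting, and no analysis step uses dose time. Any drug effect that develops between the ratings would be attributed to acupuncture.

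The size is unknown. The scenarios in the table give 3% to 63% of the interim change, but both inputs are assumed, so this range shows what cannot be ruled out and is not evidence of material bias. The direction also depends on timing.

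The point warrants a change to the plan before the final analysis: the mechanism is clear, the remedy is cheap, and a rule chosen after the final data are seen would be post hoc for a primary outcome.

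**What to change.** Amend 8.0, 11.0 and Table 1 as follows.

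1. For all acupuncture-arm patients, including those already enrolled, extract from EPIC the drug and time of every anxiolytic, sedative or opioid dose given before the second VAS. Record the clock time of both ratings where available. Classify each dose as before the first VAS or between the two.
2. Add anxiolytics, with time, to the PostAQ/PreOP row of Table 1.
3. Keep the all-patients pre/post change as the main analysis, and report the number dosed in each window beside it.
4. Before the final analysis, pre-specify two sensitivity analyses: (a) the change in patients with no dose before the second VAS, noting that this subgroup may differ from the rest; (b) all patients, with zero change assigned to those dosed between ratings, as a conservative bound. For (b) to remain a bound, an observed worsening should be left as it is.
5. State that attribution to acupuncture will be limited if these results differ materially from the main one.

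The cost is one timed field from charts already being reviewed, one table entry and a short paragraph of analysis text. It depends on EPIC holding administration times, and on rating times being recoverable for past patients; where they are not, the dose window should be reported as unknown. The downside is a possibly less favourable or less precise anxiety estimate. Whether or when any drug is given does not change.
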